### **Cardiac Autonomic Analysis**

A point-process algorithm will be used to separate the heart rate variability dynamics in the classic spectral component within the high-frequency (HF) and low frequency (LF) ranges. Differences in normalized HF [ $HF_n = (HF/(LF + HF))$ ] will be estimated during exposure to negative images in the fMRI stress task as a metric of cardiac vagal activity.

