The circuits stimulated by VNS (i.e. mood circuitry) overlap with the circuits for autonomic nervous system (ANS) regulation. Heart rate variability (HRV) is an important measure of the health of ANS. HRV analysis indirectly estimates sympathetic and parasympathetic modulation of the heart. The peak in low-frequency spectral band (LF) is thought to be influenced by both parasympathetic and sympathetic activity. The peak in high-frequency band (HF) is influenced solely by parasympathetic (vagal) activity and the LF/HF ratio approximates the balance between sympathetic and parasympathetic modulation of the heart. Deficits in vagal tone have been found in patients with MDD as evidenced by decreased HF band. Vagal output from the hypothalamus projects to the heart and releases acetylcholine to slow heart rate. Vagal afferents provide feedback regulation of the heart through the nucleus tractus solitaires, which then projects to the heart. This feedback on heart rate can come from any of the vagal afferent branches. The auricular branch of the vagus nerve is an easily accessible vagus branch that can be directly stimulated. The dorsal medullary vagal system operates in tune with respiration, and therefore stimulation gated to exhalation/inhalation might have modulatory effects on vagal tone. The systematic

study of respiratory-gated tVNS in MDD patients may reveal whether in addition to regulating mood, it can regulate HRV.

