## **II. SPECIFIC AIMS**

Major Depressive Disorder (MDD) is a leading cause of morbidity and mortality worldwide. Abnormalities in vagal tone are more common in MDD, particularly loss of parasympathetic cardiac regulation, and increase the risk for cardiovascular disease (CVD). Vagal nerve stimulation (VNS) is an FDA approved treatment for MDD that modulates circuitry implicated in mood regulation. However it is unclear whether therapeutic benefit of VNS on mood, can also reduce cardiac morbidity and mortality. The circuits for autonomic cardiac regulation overlap with those for mood regulation, but modulation of ANS has not been directly associated with mood response. As a first step, we will identify whether VNS effects on mood circuitry in MDD are associated with modulation of vagal tone and mood.

In the proposed study in MDD patients, we will 1) identify the neural circuitry associated with tVNS, 2) identify its acute effects on heart rate variability, and 3) assess the impact of brain activity and ANS function on mood. We will control for factors known to impact vagal tone, in particular gonadal hormones in women. This is the first study to map the neurobiology of mood and vagal response to VNS using a less invasive form of VNS that may have a wider application.

**Specific Aim 1:** To determine the acute effects tVNS on cerebral blood flow in MDD patients.

Hypothesis 1: During real tVNS/fMRI interleaving, tVNS will deactivate amygdala, parahippocampal gyrus, hippocampus, posterior cingulate, and precuneus and will activate insula, thalamus and anterior cingulate.

Hypothesis 2: Brain activity deficits in stress response circuitry in MDD will be attenuated following 20 minutes of tVNS, in hypothalamus, amygdala, hippocampus, and anterior cingulate gyrus.

**Specific Aim 2:** To determine the acute effects of tVNS on vagal tone and mood in MDD patients.

Hypothesis 1: tVNS will increase high frequency R-R variability and decrease mood symptoms compared to baseline.

**Specific Aim 3:** To compare the effects of exhalation-gated tVNS with inhalation-gated tVNS on cerebral blood flow, vagal tone and mood regulation in MDD patients.

Hypothesis 1: Exhalation-gated tVNS will have a significant greater impact on regulation of cerebral blood flow, vagal tone and mood in MDD patients compared to inhalation-gated tVNS.

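### The only planned HRV outcome, HFn = HF/(LF+HF), is a function of LF/HF alone, so a change in it cannot by itself be attributed to HF, the quantity Aim 2 names; log HF and log LF should be prespecified beside it

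*Combined protocol and SAP*

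**What the plan says.** Section VI, Cardiac Autonomic Analysis, is the whole cardiac plan. A point-process algorithm will "separate the heart rate variability dynamics in the classic spectral component within the high-frequency (HF) and low frequency (LF) ranges". One outcome is then defined, HFn = HF/(LF+HF), and differences in it "will be estimated during exposure to negative images in the fMRI stress task as a metric of cardiac vagal activity". No analysis of HF alone, LF alone or total power is planned anywhere. The paragraph names no test, and it does not say between which conditions the differences are taken.

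The vagal hypotheses are in section II. Aim 2 Hypothesis 1 states that "tVNS will increase high frequency R-R variability and decrease mood symptoms compared to baseline". Aim 3 Hypothesis 1 expects exhalation gating to have a "significant greater impact on regulation of cerebral blood flow, vagal tone and mood in MDD patients" than inhalation gating.

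Section I says what each spectral quantity is taken to mean:

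- HF: "The peak in high-frequency band (HF) is influenced solely by parasympathetic (vagal) activity".
- LF: "The peak in low-frequency spectral band (LF) is thought to be influenced by both parasympathetic and sympathetic activity".
- Ratio: "the LF/HF ratio approximates the balance between sympathetic and parasympathetic modulation of the heart".

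**The concern.** On the protocol's own account, HF is the vagal component, LF is mixed, and their ratio describes balance. The planned outcome is built from the ratio but is to be read as vagal activity, and it serves a hypothesis worded in terms of HF.

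Two errors of interpretation could follow. A fall in LF with HF unchanged would raise HFn and could be reported as increased vagal activity. A proportional rise in both HF and LF would leave HFn unchanged, so an increase in HF of the kind Aim 2 predicts would not be seen. The vagal conclusions of Aims 2 and 3 are at stake. The mood and fMRI analyses do not use HFn and are unaffected.

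**Working it through.** **Inputs.** The formula for HFn comes from Cardiac Autonomic Analysis. The sample size of 20 comes from Sample Size (Power Analysis). The documents state no HRV effect size, standard deviation, alpha or power; the only standard deviation given (2.5%) is for BOLD signal change. There is therefore no HRV figure in the plan to reproduce.

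**Step 1: algebra, no assumptions.** Dividing numerator and denominator by HF gives

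HFn = HF/(LF+HF) = 1/(1 + LF/HF).

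The odds are HFn/(1 − HFn) = HF/LF, so

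logit(HFn) = ln HF − ln LF.

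HFn is a strictly decreasing one-to-one function of LF/HF. A change in logit(HFn) equals the change in ln HF minus the change in ln LF, whatever the baseline.

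**Step 2: worked values.** Take the baseline odds, multiply by the factor by which HF/LF changes, and convert back. For baseline 0.50 (odds 1) and a factor of 1.2, HFn = 1.2/2.2 = 0.545.

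| Change | Factor on HF/LF | From 0.30 | From 0.50 | From 0.70 |
|---|---|---|---|---|
| HF +20%, LF unchanged | 1.2 | 0.340 | 0.545 | 0.737 |
| HF unchanged, LF −16.7% | 1/(1/1.2) = 1.2 | 0.340 | 0.545 | 0.737 |
| HF +20%, LF +20% | 1 | 0.300 | 0.500 | 0.700 |
| HF −10%, LF −30% | 0.9/0.7 = 1.286 | 0.355 | 0.563 | 0.750 |

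The first two rows cannot be told apart from HFn. In the third, HF rises and HFn does not. In the fourth, HF falls and HFn rises.

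**Step 3: illustration under assumptions.** Simulated trials of 20 within-subject changes were analysed with a paired t-test on the change in logit(HFn), two-sided 5%. Changes in ln HF and ln LF have equal SDs and correlation r, and the true mean change in ln HF is zero. The SDs, r, the shift in ln LF and the test itself are all assumed.

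| Mean change in ln LF | Significant HFn rise, r = 0 | r = 0.5 |
|---|---|---|
| 0 | 2.5% | 2.5% |
| −0.25 SD | 11% | 19% |
| −0.5 SD | 32% | 57% |

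For the −0.5 SD case the figure is about 23% at r = −0.5 and 92% at r = 0.8, so the result depends heavily on r.

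If instead ln HF and ln LF both truly rise by 0.5 SD, a significant HFn rise appears in about 2.5% of trials. A paired test on log HF would be significant in about 56%.

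**Step 4: two possible attribution rules, −0.5 SD case.** These are the proportions of trials in which a significant HFn rise would still be read as vagal.

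| Rule | r = 0 | r = 0.5 |
|---|---|---|
| No check | 32% | 57% |
| Mean log HF above zero | 27% | 36% |
| Log HF 95% CI above zero | 2.4% | 2.3% |

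A sign check is weak because a significant HFn rise itself makes a positive sample mean of log HF more likely.

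**The case against.** HFn is an openly defined choice, and it removes overall scaling. Section II does not say whether absolute, log or normalized HF is meant, so normalized HF is a permissible reading of the hypothesis. The algorithm yields HF and LF in any case, so the components could be examined later and no data are lost. This is a 20-subject mechanistic study with no power claim for HRV. The simulated percentages rest on quantities that the documents do not give.

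Most of this stands, and it limits the point. A reader might infer that HFn is invalid, or that the analysis contradicts the hypothesis. The documents support neither: they leave the form of HF open, and HFn is a legitimate measure of relative HF. A reader might also take the simulated rates as the trial's actual error rates or as bounds on them. They are neither.

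What the objection does not remove is the attribution. Section I calls LF mixed, so by the protocol's own reasoning a rise in HFn produced only by a fall in LF is not evidence of greater HF. Recovering the components afterwards would also leave the choice of HRV measure to be made with results in view.

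Log HF has its own weaknesses. Absolute HF varies more between subjects, and HF depends on breathing, which matters because section I notes that "The dorsal medullary vagal system operates in tune with respiration" and stimulation is breath-gated. The breathing problem is not peculiar to log HF, since HFn also contains HF.

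**Conclusion.** The point holds as a gap in interpretation. The algebra alone establishes that HFn is equivalent to LF/HF, and therefore that a change in HFn cannot be assigned to HF without looking at HF. No assumption is needed for that.

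Its practical size cannot be determined from the documents. In the illustration with no mean HF change and ln LF down 0.5 SD, a significant HFn rise occurs in about 23% to 92% of trials as r goes from −0.5 to 0.8. That shows the problem could be material, not how likely it is here.

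The consequence is confined to the vagal component of Aim 2 Hypothesis 1 and of Aim 3 Hypothesis 1. The change is worth making because vagal tone is a named target of two of the three aims and the correction is nearly free.

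**What to change.** Keep HFn as planned and add the following to Cardiac Autonomic Analysis:

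1. Prespecify log HF and log LF from the same point-process output and the same negative-image window. Analyse them by time (PRE, POST) and session (exhalation-gated, inhalation-gated), the layout already used for the mood and fMRI data.
2. State that log HF is the measure that tests the high-frequency wording of Aim 2. Report HFn as the balance measure and log LF as supportive. Because logit(HFn) = ln HF − ln LF, the three carry only two independent pieces of information, and naming one for the hypothesis avoids a choice among them later.
3. Attribute a rise in HFn to increased vagal activity only when the log HF 95% confidence interval for the same contrast also excludes zero in that direction. Otherwise report a change in LF/HF balance. Agreement in sign alone is not enough.
4. Report a rise in log HF without a change in HFn as an increase in HF without a change in balance.

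The cost is a few lines of text and two further summaries from components already separated. The stricter rule will more often withhold a vagal reading at n = 20, and the greater between-subject spread of absolute HF has to be accepted. Sensitivity to breathing remains for log HF and HFn alike; the respiration signal already recorded (Physiological Monitoring During fMRI Scanning) should be considered when either is interpreted.

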## **VII. RISKS AND DISCOMFORTS**

### **Blood Draw**

Subjects may feel slight discomfort when we insert the needle and draw blood through a vein. Very rarely, the vein may become sore and red. In addition, a temporary, harmless bruise may develop. Although rare, some people faint when blood is drawn. In rare cases, the subject can get an infection where the blood was drawn. The infection can usually be treated with antibiotics.

## **Saliva Collection**

At this time, there are no known risks for the saliva collection.

## **MRI Scanning**

There are no known or foreseeable hazards or risks associated with MRI imaging except for people with electrically, magnetically, or mechanically activated implants (such as cardiac pacemakers) or those who have metallic clips in their brain – all of whom would be excluded from this study. The powerful magnetic field created by the MRI can disturb these metal objects. In addition, since the effect of MRI on the fetus is unknown, women suspect pregnancy will be excluded from the study. The investigator will ask the participant if they are prone to claustrophobia, if so they will not be scanned. The participant will be asked to fill out a screening questionnaire prior to the MRI scan in order to rule out any condition that may preclude MRI scanning. Conventional MRI systems have been approved by the FDA and will be operated within the operating parameters reviewed and accepted by the FDA. The loud gradient noise if the MRI could potentially cause hearing damage if no protection were to be used, therefore, all subjects are required to wear earplugs to ensure scanner noise is reduced to safe levels. During the scan, voice contact with participants will be maintained. Participants will be instructed to notify the examiner of any discomfort. If the discomfort cannot be alleviated, the scanning session may be terminated prematurely and inquiries will be made to assess if subjects are well and comfortable.

MRI could potentially uncover an anatomic abnormality in the brain. If this occurs, the established protocol for the BWH Research Imaging Center will be followed. If any anatomic abnormality is suspected in the anatomic MRI images, the films will be reviewed by the staff radiologist in the scanning facility. The radiologist will decide whether the suspected abnormality is clinically significant and will discuss the findings as well as further recommendations with the participant.

## **tVNS Stimulation**

There is a small possibility of slight and temporary discomfort at the site where the electrodes are placed. Potential vaso-vagal reactions to stimulation resulting in dizziness or light-headedness will be promptly recognized and treated by a study physician with prompt removal of the electrodes and repositioning the subject into a supine position. In some subjects, the experience of electrical stimulation may cause anxiety. Subjects will be required to remain under supervision until all symptoms subside. A study physician will be available at all times to discuss the study with subjects should they become concerned.

In the proposed study, only non-magnetic electrodes will be used. The electrical stimulation procedure is without significant safety concerns. The electrical stimulator, checked by Biomedical Engineering, has a current limiter preventing harmful stimulation levels. Further, during the electrical stimulation, we will be closely monitoring that the current received by the subject is well tolerated. Throughout the measurement sessions, participants will be repeatedly asked if they are well and comfortable. Should the subject feel any discomfort in the fMRI measurements, she will be advised to squeeze the pneumatic signaling device (always held in her/his left hand) and the measurement will be immediately interrupted.

## **VIII. POTENTIAL BENEFITS**

There are no expected benefits for subjects participating in these studies. However, the findings of this investigation may help advance the field of developing novel therapeutics as well as our understanding of pathways that may mediate the body's mood and cardiac mechanisms. Therefore, we believe that the slight risks associated with these studies are reasonable in relation to the potential benefits.

## **IX. MONITORING AND QUALITY ASSURANCE**

The investigator in charge of the study will perform safety monitoring during the entire imaging session. The PI and co-investigators will also review the data for consistency and accuracy as well as monitor that analysis is conducted properly. Furthermore, the technical staff at the Longwood Imaging Center will continually monitor the nature and quality of the data collected using the 3T MRI scanner. The participants data will be stored in a computer network in a secure, password protected, account. The participant will be identified by a unique participant number that is linked only to their name by a master data sheet that is kept in a secure locked filing cabinet.

In the case of a serious adverse event (i.e. death, life threatening experience) the incident will be reported immediately (within 24 hours of event) by telephone, fax or e-mail followed by a full written report using the PHRC Adverse Event Form within 10 working days/14 calendar days. In the case of a mild (i.e. minor irritant type) or moderate (i.e. discomfort requiring treatment) adverse event that is unexpected but may be related to the experiment, the incident will be reported in writing using the PHRC Adverse Event Form within 20 working days/30 calendar days. In the case of a mild or moderate adverse event that is unexpected, but not related to the experiment, the PI will summarize the event in the progress report at continuing review. In the case of a mild or moderate adverse event that is expected the event will be summarized by the PI in the progress report at continuing review.
